1.3 RATIONALE

Inovio's sDNA therapy VGX-3100 has demonstrated tolerability, immunogenicity and efficacy in a randomized Phase 2b study in HPV-16/18 pre-malignant disease of the cervix, and a pilot study of INO-3106 with INO-9012 in three patients with HPV-6-related aerodigestive disease which demonstrated tolerability, immunogenicity and preliminary efficacy, specifically in two patients with RRP. RRP, although rare, continues to be diagnosed in adults and adolescents, and in children. Therapeutic treatment consists of frequently recurring surgery, and there are few other therapies currently in development. Historical or ongoing clinical studies include evaluating anti-virals (cidofovir), angiogenesis inhibitors (bevacizumab), and checkpoint inhibitors (pembrolizumab, others), and those have shown some promising results ^[2]. However, no product has been labeled for RRP. INO-3107 has the potential to generate robust T cell responses against HPV-6 and HPV-11 E6 and E7, resulting in eradication of RRP lesions and ideally, eradication of HPV-6 or HPV-11, in patients treated with INO-3107. This study will assess the safety and tolerability, immunogenicity, and efficacy of INO-3107 in adults with RRP.

This study will utilize the dose and schedule previously used in the Inovio HPV-006 study of INO-3106 and INO-9012, in which 6 mg of INO-3106 was given IM followed by EP every three weeks for four doses. In this study, 6.25 mg of INO-3107 will be given every three weeks for four doses. Subjects will be required to have demonstrated a prior history of requiring surgical intervention to manage their RRP, and follow-up will assess safety, tolerability, immunogenicity and the frequency of RRP surgical interventions post Day 0 compared to pre-dose. Patients will be followed for approximately 12 months after the first dose.

1.4 POTENTIAL BENEFITS AND RISKS

INO-3107 has the potential to treat patients with HPV-6 and/or HPV-11-associated RRP, reducing the number of surgical interventions required to control the disease, and potentially to eradicate the virus in treated patients, potentially resulting in a disease cure. This not only would reduce exposure to future inevitable surgical intervention but would also remove the signs and symptoms associated with RRP and the potential for malignant transformation and development of HPV-6- or HPV-11-associated cancer.

The risks associated with DNA therapy have been well described and are coupled with the risks of EP with the CELLECTRA® 2000 device. Over 6000 injections have been delivered and over 2000 subjects have received injections with the Inovio platform utilizing the CELLECTRA® 2000 device to date. In general, the risks associated with DNA therapy and the CELLECTRA® 2000 device are limited to localized injection reactions, including injection site pain, erythema, edema or bruising; fever, fatigue, headache, myalgia, and arthralgia have also been reported. Pain associated with the CELLECTRA® device has been well-characterized and is largely transient ^[33].

2.0 OBJECTIVES AND PURPOSE

This is a Phase 1/2 open-label, multicenter trial to evaluate the safety, tolerability, immunogenicity, and efficacy of INO-3107 in subjects with RRP.

2.1 HYPOTHESIS

INO-3107, [REDACTED] delivered intramuscularly (IM) followed by electroporation (EP) with CELLECTRA® 2000 will be generally safe and well-tolerated in subjects with recurrent respiratory papillomatosis secondary to HPV-6 and/or HPV-11.

3.0 CLINICAL TRIAL DESIGN AND ENDPOINTS

This is a Phase 1/2 open-label, multicenter trial to evaluate the safety, tolerability, immunogenicity, and efficacy of INO-3107 in subjects with RRP. INO-3107 will be administered IM followed by EP in subjects at Day 0, Weeks 3, 6, and 9. Approximately 20 subjects will receive INO-3107 via standard needle, followed by approximately 10 subjects who will receive INO-3107 via the Side Port Needle.

This trial will enroll approximately 30 adults (≥ 18 years old) who have been diagnosed with either Juvenile-Onset RRP (J-O RRP) as defined by age at first diagnosis < 12 years or Adult-Onset RRP (A-O RRP) as defined by age at first diagnosis ≥ 12 years.

This study will have a safety-run in:

Up to six, subjects will be enrolled with a one week waiting period between each enrolled subject. Each subject will be assessed up to Week 6. Once the first three subjects of up to these six have completed Week 6 assessments, in the absence of dose-limiting toxicity (DLT), subject enrollment may begin in full after review of safety data and discussion between the Sponsor's Medical Monitor and the Investigator's at the subjects' site. However, if prior to the first three to six subjects completing Week 6, a single subject from the first six experiences a DLT then enrollment will be limited to six subjects until all six subjects have reached Week 6 and are assessed for DLT.

If a second subject within the first 6 experiences a DLT within the first 6 weeks, enrollment will stop, and the Sponsor's Medical Monitor and Investigator(s) at the subjects' site(s) will discuss the case, and a decision will be made whether to cease further enrollment. If a change to the protocol is required, enrollment will only be re-initiated after amendment of the protocol and approval of the amended protocol by the respective study IRBs.

Enrollment will continue until approximately 30 subjects are enrolled.

Safety and tolerability will continue to be assessed throughout the study after tolerability has been established in the first six subjects. If more than two subjects experience a DLT at any time during the study, after the initial six subjects are enrolled, the Sponsor will pause enrollment until further discussion with the site Investigator determines that the study may reopen to enrollment.

Tolerability will be determined by the reported incidence of dose-limiting toxicity (DLT), which is defined as:

- Treatment-related NCI Common Terminology Criteria for Adverse Events (CTCAE, version 5.0) Grade ≥ 3 non-hematological toxicity that does not respond to supportive therapy and lasts for longer than 48 hours, or;

- Treatment-related NCI CTCAE v5.0 Grade ≥ 3 hematological toxicity that does not respond to supportive therapy and lasts for longer than 48 hours.

Additionally, enrollment and additional dosing will be paused until Sponsor discussion with the site Investigator determines that enrollment and dosing may continue, if the following CTCAE v5.0 events occur at any time in the study:

- One Grade 4 or 5 related SAE;
- Two Grade 3 related SAEs

Subjects will undergo routine surgical procedure for removal of papilloma(s) during the screening period within 14 days prior to Day 0 dosing (papilloma removal and Day 0 dose may be performed same day if other eligibility criteria have been fulfilled). Biopsy tissue will be collected and sent to [REDACTED] for evaluation of secondary [REDACTED] endpoints. Archival tissue (slides or blocks) obtained within one year of the screening window may be used, or a biopsy conducted during routine surgery.

Status of disease during the trial will be monitored by the Investigator during laryngoscopy including documentation with Staging Assessment scores. If at any time during the trial, surgical removal (including laser) of papilloma is clinically indicated per PI judgement, the subject may undergo procedure for papilloma removal but this must be captured on the electronic case report form. Documentation of the Staging Assessment score prior to surgery is required, and explanation for requirement of surgical removal of papilloma must be documented.

Surgical interventions during the trial must be documented to include at a minimum, information about the appearance and location of tissue being removed and instruments used. Video/photographic documentation of laryngoscopy is required.

This trial will not utilize a Data Safety Monitoring Board. This is a single-arm, open-label trial. The Sponsor will have access to unblinded safety and tolerability data during the trial. At a minimum, the Sponsor's Medical Monitor will review reported adverse events quarterly.

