5.2 TREATMENT REGIMEN

Subjects will be administered one 6.25 mg injection of INO-3107 IM followed by EP at Day 0, Week 3, Week 6, and Week 9.

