- Document any present conditions and concomitant illnesses;
- Record current concomitant medications/treatments ([Section 6.13](#));
- Targeted physical examination ([Section 6.4.1](#));
- Record vital signs ([Section 6.4.2](#));
- Record body weight, height and determine BMI ([Section 6.4.3](#));
- Safety labs collected within 72 hours prior to dosing such that results are available and assessed against DLT criteria prior to dosing ([Section 6.4.4](#));
- Collect urine for urine pregnancy test, if applicable ([Section 6.4.4](#));
- Collect whole blood [REDACTED] for immunology assessment ([Section 6.10](#)).
- Laryngoscopy and Staging assessment ([Section 6.4.5](#)).
 - If it is the Investigator's practice to routinely biopsy during laryngoscopy, this should be performed at this visit.

The following evaluations will be performed **after IP administration**:

- Collect any new adverse events;
- Download EP Data ([Section 6.5.1](#)).

6.1.2.4 Week 9

The following evaluations will be performed **prior to IP administration**:

- Collect all present and/or new or ongoing adverse events;
- Document any present conditions and concomitant illnesses;
- Record current concomitant medications/treatments ([Section 6.13](#));

- Targeted physical examination ([Section 6.4.1](#));
- Record vital signs ([Section 6.4.2](#));
- Record body weight, height and determine BMI ([Section 6.4.3](#))
- Safety labs collected within 72 hours prior to dosing such that results are available and assessed against DLT criteria prior to dosing ([Section 6.4.4](#));
- Collect urine for urine pregnancy test, if applicable ([Section 6.4.4](#));
- Collect whole blood [REDACTED] for immunology assessment ([Section 6.10](#)).

The following evaluations will be performed **after IP administration**:

- Collect any new adverse events;
- Download EP Data ([Section 6.5.1](#)).

6.1.2.5 Week 11

The following evaluations will be performed at this visit:

- Collect all present and/or new or ongoing adverse events;
- Document any present conditions and concomitant illnesses;
- Record current concomitant medications/treatments ([Section 6.13](#));
- Collect whole blood [REDACTED] for immunology assessment ([Section 6.10](#));
- Laryngoscopy and Staging assessment ([Section 6.4.5](#)).
 - If it is the Investigator's practice to routinely biopsy during laryngoscopy, this should be performed at this visit.

6.1.2.6 Week 26

The following evaluations will be performed at this visit:

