7.9 SAFETY DATA REPORTING PERIOD, METHOD OF COLLECTION AND SUBMISSION

All AEs will be collected from the time when informed consent is obtained to Week 52 or at participant's last visit due to early discontinuation. This information will be captured in the Electronic Data Capture (EDC) system.

If the PI determines that the AE meets serious criteria, then the AE will be recorded as an SAE.

SAEs and DLTs will be reported to the Sponsor from the time the subject signs the informed consent until Week 52 or at participant's last visit due to early discontinuation.

All SAEs (regardless of causal relationship) and DLTs, will be reported on the SAE Report Form and submitted to the Sponsor within 24 hours of becoming aware of the event.

The original SAE Report Form must be kept at the clinical trial site.

The event will be data entered into the EDC.

For the events that are considered a DLT, the PI will contact the Sponsor within 24 hours of becoming aware of the event to discuss whether dosing should continue.

SAE Contact Information

Safety Email:	
Safety Fax:	
Safety Phone:	

Medical Monitor Direct contact Information

Medical Monitor:		M.D.
Email:		
Cell Phone:		

All SAEs, and DLTs must be followed by the PI until resolution or return to baseline status, or stabilization of the event (i.e., the expectation that it will remain chronic), even if it extends beyond the clinical trial reporting period.

Follow-up information is to be submitted to the Sponsor on an SAE Report Form and within 24 hours of becoming aware of the information.

If medical records are submitted to the Sponsor with the SAE Report Form, the clinical trial site must:

- Redact the medical records of all personal data (e.g., confidential subject data, Personal Identifying Information (PII))
- Provide the assigned clinical trial subject number (SID) on the records

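### The run-in two-DLT stop covers only the first 6 weeks, mainly doses 1–2 of 4, so a second DLT after doses 3–4 can wait for a third before an enrolment review is required

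*Protocol*

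**What the plan says.** Four rules bear on DLTs or related toxicity (Protocol synopsis and Section 3.0; SAP 1.2.1).

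- **Two-DLT stop.** "If a second subject within the first 6 experiences a DLT within the first 6 weeks, enrollment will stop", followed by a discussion between the Medical Monitor and the investigators. SAP 1.2.2 restates it as two subjects with a DLT inside 6 weeks.
- **One-DLT cap.** After a single DLT before the run-in subjects complete Week 6, "enrollment will be limited to six subjects until all six subjects have reached Week 6 and are assessed for DLT".
- **Later pause.** "If more than two subjects experience a DLT at any time during the study, after the initial six subjects are enrolled", the Sponsor pauses enrolment.
- **SAE pause.** One related SAE of Grade 4 or 5, or two of Grade 3, pauses enrolment and dosing (also Protocol 7.8.3).

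Full enrolment may open early: "Once the first three subjects of up to these six have completed Week 6 assessments" without a DLT, and the safety data have been reviewed, recruitment is no longer restricted.

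Treatment is given "IM followed by EP at Day 0, Week 3, Week 6, and Week 9" (Protocol 5.2). At the Week 6 visit the checks before dose 3 include: "Safety labs collected within 72 hours prior to dosing such that results are available and assessed against DLT criteria prior to dosing" (Protocol 6.1.2.3). A DLT is a related toxicity of Grade 3 or higher that persists beyond 48 hours despite supportive care. It need not be serious.

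For each DLT, "the PI will contact the Sponsor within 24 hours of becoming aware of the event to discuss whether dosing should continue" (Protocol 7.9). There is no DSMB, and the Medical Monitor reviews adverse events at least quarterly.

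**The concern.** The same signal, two of six subjects with a DLT, is handled differently according to when it appears. If both DLTs are early, enrolment stops for a joint review. If the second follows dose 3 or 4, it falls outside the 6-week window, two subjects are too few for the later pause, and non-serious events do not count toward the SAE pause. Recruitment can then continue until a third subject has a DLT. The documents give no reason for treating the second half of the regimen more leniently, and safety is the primary objective.

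**Working it through.** **Plan's own figures.** None is given for the DLT rules. The only computable safety figure is the SAE bound in SAP 3.1 (below 12% with n=30). It reproduces as the exact two-sided 95% limit for 0/30: 1 − 0.025^(1/30) = 11.57%. It is not used below.

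**Rule check (needs no assumed rate).** Take two of the first six with non-serious Grade 3 DLTs, the second after 6 weeks.

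- Two-DLT stop: the second DLT is outside the window, so it is not met.
- Later pause: 2 is not more than 2, so it is not met.
- SAE pause: no SAEs, so it is not met.
- One-DLT cap: it may hold enrolment at six, but it lifts once all six reach Week 6 and requires no review of a later second DLT.

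**Calendar at the minimum 7-day stagger.**

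- Third subject's Week 6, when full enrolment can open: 14 + 42 = day 56.
- First dose 4 of any subject: day 63.
- Sixth subject's Week 6, when the cap lifts: 35 + 42 = day 77.
- Sixth subject's dose 4: 35 + 63 = day 98.

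**How far the window reaches.** Dose 3 is nominally on day 42, after the Week 6 check. The ±4-day visit window allows it on day 38, and 38 + 2 = 40, so a dose-3 DLT can pass 48 hours before day 42. The stop therefore covers mainly, not only, doses 1–2.

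**Size.** The documents give no DLT rate. Protocol 1.4 says platform risks in general "are limited to localized injection reactions, including injection site pain, erythema, edema or bruising", with some systemic symptoms also reported. I therefore assume a constant per-dose risk d of 1–2%, with 5% and 10% as hypothetical stress values. Let p2 = 1 − (1−d)^2, p4 = 1 − (1−d)^4 and q = p4 − p2.

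- Pattern (exactly two of six, at most one in doses 1–2): 15(1−p4)^4(p4² − p2²)
- Mixed (one early, one late): 15(1−p4)^4 · 2·p2·q
- Both late: 15(1−p4)^4 · q²
- Third DLT among 24 later subjects: 1 − (1−p4)^24
- Median further subject with the third DLT: ln 0.5 / ln(1−p4), rounded up
- Two-or-more rule firing: P(X ≥ 2), X binomial with n = 6, using p2 (current window) or p4 (all four doses)

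| d | 1% | 2% | 5% | 10% |
|---|---|---|---|---|
| p2 | 0.0199 | 0.0396 | 0.0975 | 0.1900 |
| p4 | 0.0394 | 0.0776 | 0.1855 | 0.3439 |
| Pattern | 1.5% | 4.8% | 16.4% | 22.8% |
| of which mixed | 1.0% | 3.3% | 11.3% | 16.3% |
| of which both late | 0.5% | 1.6% | 5.1% | 6.6% |
| Third DLT in 24 later | 62% | 86% | 99% | >99.9% |
| Pattern and no third DLT | 0.6% | 0.7% | 0.1% | <0.01% |
| Median further subject | 18th | 9th | 4th | 2nd |
| Rule fires, current window | 0.6% | 2.1% | 10.9% | 32.0% |
| Rule fires, four doses | 2.1% | 7.3% | 30.9% | 66.9% |

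Worked at d = 1%: 15 × 0.9606^4 × (0.0394² − 0.0199²) = 0.0148. With no third DLT: 0.0148 × (1 − 0.619) = 0.0056.

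The pattern row is an upper bound in two ways. It keeps serious DLTs, some of which would trigger the SAE pause. It also counts a late first DLT followed by an early second one, which the protocol wording catches; in a simulation at 5–10% per dose that order made up 3–4% of pattern cases. The no-third row assumes both run-in DLTs count toward the more-than-two total.

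**The case against.** The best defence is that this is a deliberate sequence: a short early window, then a higher threshold as the denominator grows. The trial tests one fixed regimen, not an escalation. Its dose and schedule are taken from a pilot judged tolerable, and over 2000 subjects have been treated on the platform. Every DLT is reported within 24 hours with direct contact about dosing, and the Sponsor can stop the trial at any time. On the calendar above, 7 of the 12 late doses (dose 3 for subjects 1–5, dose 4 for subjects 1–2) are given before day 77, so in mixed cases they fall while the cap, if triggered, still holds.

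All of this stands, and it keeps the point small. It does not supply a required enrolment review: the 24-hour contact concerns dosing, and the cap lapses without one.

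Three stronger readings are tempting, and the documents do not support them.

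- A reader might infer that any pair with one late DLT escapes the stop. The protocol wording requires only the second subject's DLT to be early, so a late first DLT followed by an early second one triggers it. Only SAP 1.2.2 reads as needing both early, and the protocol governs enrolment.
- A reader might infer that dose 3 is always outside the window. The −4-day allowance at Week 6 can bring it in.
- A reader might infer that late DLTs go unnoticed or never lead to a pause. Protocol 7.9 rules out the first. As to the second, a third DLT usually triggers the existing pause.

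A fair criticism of the remedy is that two DLTs in the first six could pause a trial with many more enrolled, while two among later subjects would not. That asymmetry would be extended, although the plan already has it in the early window.

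**Conclusion.** The point holds as a minor, cheap improvement, not as an error in the plan. When the second of two non-serious Grade 3 DLTs in the first six comes after 6 weeks (under SAP 1.2.2, when either does), no rule requires an enrolment review before a third DLT. The harm is a later mandatory review.

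This logic follows from the text alone. The size rests on assumptions: a constant, independent per-dose risk of 1–2% and 24 later subjects at the same risk. On that basis at most 1.5–4.8% of trials show the pattern. About two thirds of these are mixed cases in which the cap normally gives temporary cover, and 0.6–0.7% of trials show the pattern with no later pause. If only DLTs arising after the sixth enrolment count toward the later pause, some early run-in DLTs would drop out and the last figure would be larger.

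**What to change.** Leave the timing of full enrolment, the one-DLT cap and the more-than-two rule as they are. Reword the two-DLT rule in the synopsis and Section 3.0: when a second subject among the first six dosed has a DLT, at any time through 30 days after that subject's last dose, further enrolment pauses for the existing Medical Monitor and investigator review. The 30 days match the TEAE window in Protocol 8.5.1. Conform SAP 1.2.1 and 1.2.2; the protocol text is the operative change, since the SAP does not control enrolment.

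The cost is wording plus an occasional extra discussion. At 1% per dose the rule fires in 2.1% instead of 0.6% of trials, and at 2% in 7.3% instead of 2.1%: about 1.5 to 5 percentage points more often. At the minimum stagger the window closes on day 98 + 30 = 128, so some of these pauses would come after more than six subjects are enrolled.

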This study will enroll approximately 30 adults (≥ 18 years old) who have been diagnosed with either Juvenile-Onset RRP (J-O RRP) as defined by age at first diagnosis < 12 years or with Adult-Onset RRP (A-O RRP) as defined by age at first diagnosis ≥ 12 years.

This study will have a safety-run in:

Up to six subjects will be enrolled with a one week waiting period between each enrolled subject. Each subject will be assessed up to Week 6. Once the first three subjects of up to these six have completed Week 6 assessments, in the absence of dose-limiting toxicity (DLT), subject enrollment may begin in full after review of safety data and discussion between the Sponsor's Medical Monitor and the Investigator(s) at the subjects' site. However, if prior to the first three to six subjects completing Week 6, a single subject from the first six experiences a DLT then enrollment will be limited to six subjects until all six subjects have reached Week 6 and are assessed for DLT.

If a second subject within the first 6 experiences a DLT within the first 6 weeks, enrollment will stop, and the Sponsor's Medical Monitor and Investigator(s) at the subjects' site(s) will discuss the case, and a decision will be made whether to cease further enrollment. If a change to the protocol is required, enrollment will only be re-initiated after amendment of the protocol and approval of the amended protocol by the respective study IRBs.

Enrollment will continue until approximately 30 subjects are enrolled.

Safety and tolerability will continue to be assessed throughout the study after initial tolerability has been established in the first six subjects. If more than two subjects experience a DLT at any time during the study, after the initial six subjects are enrolled, the Sponsor will pause enrollment until further discussion with the site Investigator determines that the study may reopen to enrollment.

Tolerability will be determined by the reported incidence of dose-limiting toxicity (DLT), which is defined as:

- Treatment-related NCI Common Terminology Criteria for Adverse Events (CTCAE, version 5.0) Grade ≥ 3 non-hematological toxicity that does not respond to supportive therapy and lasts for longer than 48 hours, or;
- Treatment-related NCI CTCAE v5.0 Grade ≥ 3 hematological toxicity that does not respond to supportive therapy and lasts for longer than 48 hours.

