4.3.1 CRITERIA FOR DISCONTINUATION OF INVESTIGATIONAL PRODUCT

A subject should not receive any further investigational product (IP) if any of the following occur:

- Subject withdrawal of consent or subject is lost to follow up
- An AE that, in the opinion of the investigator or the Sponsor, contraindicates further dosing of any trial medication
- Pregnancy
- Subject non-compliance that, in the opinion of the Investigator or Sponsor, warrants discontinuation
- Initiation of new contraindicated therapy

In the absence of any of the above criterion, if limited clinical benefit is suspected at any time, IP may be discontinued after consultation between the Investigator and the Medical Monitor.

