7.8 SAFETY AND TOXICITY MANAGEMENT

The Medical Monitor is responsible for the overall safety monitoring of the clinical trial.

Safety monitoring assessments include but are not limited to:

- Incidence of all adverse events classified by system organ class (SOC), preferred term, severity and causal relationship to clinical trial IP administration
- Changes in laboratory parameters
- Local and systemic injection site review; special attention will be paid to the examination of the injection site
- Dose Limiting Toxicities (DLT)

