7.8.1 Dose Limiting Toxicity (DLT)

For the purpose of this clinical trial, the following are DLTs and are to be reported to the Sponsor in accordance with [section 7.9](#): Safety Data Reporting Period, Method of Collection and Submission.

- ≥Grade 3 non-hematological toxicity (graded per CTCAE v. 5.0) that does not respond to supportive therapy and lasts for longer than 48 hours
- ≥Grade 3 hematological toxicity (graded per CTCAE v. 5.0) that does not respond to supportive therapy and lasts for longer than 48 hours

Refer to [Section 3.0](#) for information about management of DLTs.

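### The two DLT-count rules act on enrolment only, with no automatic hold on dosing, and the later rule does nothing once enrolment is full

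*Protocol*

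**What the plan says.** Protocol Section 3.0 has two rules that depend on a count of subjects with a DLT.

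- **Run-in:** "If a second subject within the first 6 experiences a DLT within the first 6 weeks, enrollment will stop". The Medical Monitor and investigators then confer, and "a decision will be made whether to cease further enrollment".
- **Later:** with more than two DLT subjects, "after the initial six subjects are enrolled, the Sponsor will pause enrollment until further discussion with the site Investigator determines" that it may reopen. The synopsis has the same rule: "the Sponsor will pause enrollment until further discussion with the site Investigator determines that the study may reopen to enrollment".

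A third rule covers related SAEs (one of Grade 4 or 5, or two of Grade 3). It pauses further dosing as well as enrolment until the Sponsor and site investigator agree that both may resume. It stands in the synopsis, in Sections 3.0 and 7.8.3, and in SAP 1.2.1 and 1.2.2.

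Section 7.8.1 sends DLT reporting to Section 7.9 and points to Section 3.0 "for information about management of DLTs". Section 7.8.3, which holds the stopping rules, lists only the SAE triggers. SAP 1.2.2 says that a review after a pause may end enrolment permanently; it does not mention dosing.

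**The concern.** A DLT is a treatment-related toxicity of Grade 3 or higher that lasts more than 48 hours and does not respond to supportive treatment. Section 3.0 makes DLT incidence the measure of tolerability, which is part of the primary endpoint. Yet reaching either DLT count does not by itself hold the remaining doses of other enrolled subjects, whereas two related Grade 3 SAEs do.

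The later rule has a further weakness. It applies throughout the study, but enrolment closes at about 30 subjects. Pausing a closed enrolment changes nothing, and subjects who entered in the preceding 9 weeks are still being dosed. The last 10 or so subjects are the Side Port Needle group. If the count is reached at that stage, whether others go on being dosed rests on case-by-case discussion, not on a default.

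**Working it through.** **1. Rules side by side**

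| Trigger | Enrolment | Dosing of other subjects |
|---|---|---|
| Second DLT in the first six, within 6 weeks | stops | not mentioned |
| More than two DLT subjects later | paused | not mentioned |
| One Grade 4-5 or two Grade 3 related SAEs | paused | paused |

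The plan gives no figure on this point to reproduce. The rest sizes the gap. The dose schedule (weeks 0, 3, 6, 9), the one-week run-in stagger and the target of 30 come from the protocol. The DLT rates, accrual rates, recognition delay and SAE overlap are assumptions.

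**2. Run-in doses exposed**

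With six subjects entering at weeks 0 to 5, the doses left at week 5 are 2, 2, 2, 3, 3, 3, a total of 15 out of 24. Removing any two DLT subjects takes away 4 to 6 doses and leaves 9-11 in the other four.

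Two DLT subjects, each after dose 1 or dose 2, give 15 pairs × 4 = 60 cases. Assume a DLT is recognised 2.5 days after the dose. All six are already enrolled unless both causal doses fall by week 4. The number of such doses per subject is 2, 2, 1, 1, 1, 0, so the excluded cases number (7² − 11)/2 = 19, where 11 is the sum of squares. That leaves 60 − 19 = 41 cases in which all six are already in, with 5-11 doses (mean 8.2) due in the four subjects without a DLT.

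**3. Chance of the run-in trigger**

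If DLTs are equally likely after each of four doses, half the per-subject risk falls within 6 weeks. With n = 6, P(X ≥ 2) = 1 − (1−p)⁶ − 6p(1−p)⁵:

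- overall rate 1%, p = 0.005: 0.0004
- overall rate 5%, p = 0.025: 0.0088
- overall rate 10%, p = 0.05: 0.0328

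**4. Chance of the late case**

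This was simulated (1,000,000 runs at 1%; 400,000 at 5% and 10%), with the later 24 subjects entering from week 8. The event is that the third DLT among those 24 falls after last entry with doses still due.

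| Accrual per week | 1% | 5% | 10% | Mean doses left | Of these, in subjects without a DLT |
|---|---|---|---|---|---|
| 1/3 | 0.0004 | 0.023 | 0.063 | 3.8-3.9 | 2.6-2.7 |
| 1/2 | 0.0005 | 0.028 | 0.077 | 5.6-5.7 | 4.4-4.5 |
| 1 | 0.0009 | 0.050 | 0.148 | 9.4-10.2 | 8.1-8.9 |
| 2 | 0.0013 | 0.082 | 0.269 | 16.4-18.9 | 14.7-17.0 |

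If run-in DLTs also count towards the threshold (run-in gates ignored), the ranges are 0.0007-0.0023, 0.027-0.107 and 0.055-0.260, with 3.8-19.7 doses left.

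**5. Overlap with the SAE rule**

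Take three Grade 3 DLTs, each a related SAE with probability q. The SAE rule has not fired if at most one is an SAE: (1−q)³ + 3q(1−q)². For q = 0.25, 0.50 and 0.75 this is 0.844, 0.500 and 0.156. The net range for the later 24 runs from the lowest chance × 0.156 to the highest × 0.844:

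- 1%: 0.0004 × 0.156 = 0.00006 to 0.0013 × 0.844 = 0.0011
- 5%: 0.023 × 0.156 = 0.004 to 0.082 × 0.844 = 0.069
- 10%: 0.063 × 0.156 = 0.010 to 0.269 × 0.844 = 0.227

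**The case against.** The strongest reply is that dosing after a DLT is already handled, and sooner. Section 7.9 makes the investigator contact the Sponsor within 24 hours of every DLT to discuss whether dosing goes on, and that text is not limited to the affected subject. Two or three such discussions will have been required by the time a count is reached. Section 4.3.1 stops the product for "An AE that, in the opinion of the investigator or the Sponsor, contraindicates further dosing of any trial medication". Under Section 7.8, "The Medical Monitor is responsible for the overall safety monitoring of the clinical trial". Section 6.4.4 has pre-dose labs checked against DLT criteria, and Section 7.15 lets the Sponsor end the trial for safety. The SAE pause itself is lifted by discussion between essentially the same parties, so what is missing is a default state and not a new decision. A tiered rule, under which non-serious DLTs pause enrolment only, can also be defended.

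The size is uncertain too. Section 1.4 says the risks are in general "limited to localized injection reactions, including injection site pain, erythema, edema or bruising", with some systemic symptoms also reported, across more than 2000 subjects. That gives no support to a 10% DLT rate. At 5% and slow accrual the late case has a chance of 2.3-2.8%, or an expected 0.023 × 2.6 ≈ 0.06 to 0.028 × 4.5 ≈ 0.13 doses per trial in unaffected subjects, before SAE overlap. The overlap model leaves out Grade 4-5 DLTs and related SAEs that are not DLTs, both of which would narrow the gap. Finally, the abbreviation list names a Safety and Medical Monitoring Plan that was not supplied and is not cited in the body; it could add DLT actions.

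These points stand, and they limit the urgency. None of the provisions in the supplied documents makes a cluster of DLTs hold other subjects' doses by default, and none gives the later rule any effect after enrolment closes.

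**Conclusion.** The concern holds on the text, and the reading does not depend on any assumed rate. Its practical size does. Net of SAE overlap, the late case has a chance of about 0.01-0.1% at a 1% DLT rate, 0.4-7% at 5% and 1-23% at 10%; the upper ends need the fastest accrual and the lowest overlap. The run-in trigger fires in 0.04%, 0.9% or 3.3% of trials. The late window lasts at most about 9 weeks after the last Day 0. This is a modest but real gap in a safety rule, limited to DLTs that include no related Grade 4-5 SAE and fewer than two related Grade 3 SAEs. It is worth closing because closing it is cheap. Confidence is medium, since the monitoring plan was not available.

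**What to change.** In the synopsis, Section 3.0 and Section 7.8.3, give both DLT-count triggers the action already written for the SAE triggers: enrolment and further dosing pause until the Sponsor and site investigator agree that both may continue. The existing discussions then decide on dosing as well. Keep the run-in condition that enrolment restarts only after amendment and IRB approval when a protocol change is needed. Leave the single-DLT run-in rule as it is, so that all six subjects can be assessed to Week 6. Align SAP 1.2.1 and 1.2.2 for consistency only, since the SAP does not direct dosing.

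No committee, visit or subject is added. A cost arises only if a trigger fires. A short delay may push doses outside the ±4-day window and remove some subjects from the per-protocol set (Section 8.4). It may also shift dose-to-sample timing for immunogenicity, where samples count only within 7 days of the visit (Section 8.5.2.2). That is a small price against dosing on by default through an unresolved cluster of DLTs.
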